9.1.3	Confidentiality and Privacy	
9.1.4	Quality Assurance and Quality Control	18
9.1.5	Data Handling and Record Keeping	19
9.1.6	Protocol Deviations	19
9.1.7	Conflict of Interest Policy	19
9.2	Abbreviations	
10 RE	FERENCES	22

STATEMENT OF COMPLIANCE

The trial will be conducted in accordance with International Conference on Harmonisation Good Clinical Practice (ICH GCP) and applicable United States (US) Code of Federal Regulations (CFR). The Principal Investigator will assure that no deviation from, or changes to, the protocol will take place without prior documented approval from the Institutional Review Board (IRB), except where necessary to eliminate an immediate hazard(s) to the trial subjects. All personnel involved in the conduct of this study have completed Human Subjects Protection and ICH GCP Training.

The protocol, informed consent form(s), recruitment materials, and all subject materials will be submitted to the local Institutional Review Board (IRB) for review and approval. Approval of both the protocol and the consent form must be obtained before any subject is enrolled. Any amendment to the protocol will require review and approval by the IRB before the changes are implemented to the study. All changes to the consent form will be IRB approved; a determination will be made regarding whether a new consent needs to be obtained from subjects who provided consent, using a previously approved consent form.

[figure not shown]
1 PROTOCOL SUMMARY

1.1 SYNOPSIS

Title:	Testing scalable, IVR-supported cancer prevention interventions in the rural Alabama Black Belt
Study Description:	This protocol involves a randomized controlled trial (N=240) to test the efficacy of the Deep south Active Lifestyle (DIAL intervention) telephone-based physical activity counseling intervention vs. a wait list condition. Assessments of MVPA and psychosocial variables will occur at baseline, 6, 12, and 18 months.
	Primary aim. Test the efficacy of DIAL intervention vs. wait list control. Hypotheses are that the participants receiving DIAL intervention will report significantly greater increases in MVPA (based on 7-Day Physical Activity Recalls, accelerometers) from baseline to 6 and 12 months than the wait list control arm.
	Exploratory Aims. Examine 1) Intervention effects on physical performance and psychosocial variables (anxiety, depression, fatigue, sleep disturbance; corroborate self report sleep improvements from pilot with accelerometry); 2) Changes in MVPA from 12-18 months to assess long term (6 months post-intervention) maintenance in the intervention arm and ascertain replicability of intervention effects in wait list control arm; 3) Intervention costs; 4) Potential mediators (social support from family, friends, CHAs, theoretical constructs directly targeted by the intervention) and moderators (education, neighborhood/environmental features) of treatment efficacy; 5) Potential barriers/ facilitators to widespread implementation of DIAL intervention in rural Black belt counties by Deep South Network for Cancer Control.

Objectives:	This proposal tests an intervention which acts on multiple levels of the socio-ecological model and uses IVR technology to enhance the potential for scaling and sustainability for broad use in populations at high risk for sedentary behavior (residents of rural Black counties in the Deep South).
Endpoints:	Changes in physical activity (as measured by 7-Day Physical Activity Recall
	interview) over time.
Study Population:	Adults
Phase:	2/3
Description of Study Intervention:	Deep south Interactive voice response system Active Lifestyle (DIAL) intervention. Participants will receive 12 months of automated physical activity phone counseling. Participants will report their physical activity to the IVR system each day for 3 months, twice/week in months 3-6, and once/week in months 6-12 and receive progress feedback via IVR system, along with community health worker support.
Study Duration:	5 year project period
Subject Duration:	18 months

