3 STUDY DESIGN

3.1 OVERALL DESIGN

The current study will test the efficacy of a 12-month multi-level, Interactive Voice Response system-supported physical activity intervention vs. a waitlist control condition. Primary endpoints are changes in moderate intensity or greater aerobic physical activity from baseline to 6 months and 12 months. Secondary endpoints include examining effects on physical performance and related psychosocial variables; intervention costs, changes in physical activity from 12-18 months, potential mediators/moderators of intervention efficacy, and barriers and facilitators to the implementation and sustainability of the DIAL intervention. This two armed randomized controlled trial will enroll a sample of 240 underactive adults from rural Black Belt (Marengo, Choctaw, Sumter, Hale, Greene, Dallas) counties in Alabama. Interested individuals will attend study information sessions hosted by local county coordinators to learn more about the study and complete brief screening interviews.

If still eligible and interested, participants will complete the informed consent process and be scheduled for an assessment visit. At this visit, participants will complete measurements (height, weight, waist circumference, 2 Minute Step Test, psychosocial surveys in REDCap) at a community location with their local county coordinator. Accelerometers will be distributed with instructions and a live demonstration of proper wear. Trained UAB staff will coordinate accelerometer data collection (device initialization, delivery, maintenance, etc). Participants will wear the accelerometer for 7 days. Once valid wear protocol is confirmed, participants will complete 7-Day Physical Activity Recall interviews by phone with trained, blinded UAB research

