staff. After all assessment measures are complete, participants will be randomly assigned to a group. Intervention participants will receive orientation to the IVR system and begin the physical activity intervention and the Waitlist Control participants will be encouraged to maintain their normal routine until 6 month assessments. At 6-, 12-, and 18- months, participants will repeat accelerometer wear protocols, 7-Day Physical Activity Recall interviews (by phone), and inperson assessment visits (weight, waist circumference, 2 Minute Step Test, psychosocial surveys) with local staff. Psychosocial surveys will also be distributed at 3-months to a assess potential mediators/ moderators of treatment efficacy. Participants will also complete surveys and exit interviews to assess program satisfaction and solicit feedback for improvement (at 12 months for the intervention arm and 18 months for the waitlist control arm). The wait-control group will be offered the 12 month DIAL intervention (same as intervention arm) after the 6 month assessment.

Throughout the project period, UAB research staff and Office of Community Outreach and Engagement county coordinators will report study progress via weekly emails and Zoom meetings. Surveys and in-depth qualitative interviews with participating Office of Community Outreach and Engagement county coordinators will be held to reflect on barriers and facilitators to implementing IVR-supported cancer prevention interventions in rural Black Belt counties, as well as issues surrounding sustainability and future large scale dissemination.

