5.1.2 DOSING AND ADMINISTRATION

Participants will complete IVR calls each day for 3 months, twice/week in months 4-6, and once/week in months 7-12.

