8.3.5 BASELINE DESCRIPTIVE STATISTICS

The characteristics of the study populations will be summarized for each study arm using descriptive statistics, such as means and SD for continuous variables and frequencies and proportions for categorical variables. Unadjusted comparisons of baseline characteristics between study arms and those between participants who completed the study and those who dropped out will be performed using the two-group t test for continuous variables and the Pearson chi-square test for categorical variables. Unadjusted within-group changes (from baseline to postintervention) will be assessed using the paired t test.

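### Exploratory aim 2 reads replication in the wait list arm over study months 12-18, which are that arm's programme months 7-12; its reference visit should be month 6.

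*Combined protocol and SAP*

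**What the plan says.** - **The aim.** Section 1.1, exploratory aim 2: "Changes in MVPA from 12-18 months to assess long term (6 months post-intervention) maintenance in the intervention arm and ascertain replicability of intervention effects"; the sentence goes on to place the replication in the wait list arm. Section 3.1 lists "changes in physical activity from 12-18 months" among the secondary endpoints, without mentioning replication or the wait list arm.
- **When the wait list arm gets DIAL.** Section 3.1: "Waitlist Control participants will be encouraged to maintain their normal routine until 6 month assessments", and then "The wait-control group will be offered the 12 month DIAL intervention (same as intervention arm) after the 6 month assessment". The exit survey and interview fall "at 12 months for the intervention arm and 18 months for the waitlist control arm", which agrees with a programme that runs over study months 6 to 18 in that arm.
- **Intensity of contact.** Section 5.1.2: "Participants will complete IVR calls each day for 3 months, twice/week in months 4-6, and once/week in months 7-12".
- **Visits.** Section 1.1: "Assessments of MVPA and psychosocial variables will occur at baseline, 6, 12, and 18 months".
- **Analyses of within-group change.** Section 8.3.2 fits a repeated-measures mixed model to all four visits and describes within-group change as running from baseline to follow-up. Section 8.2 powers a paired t test of the DIAL arm's change to 6 months. Section 8.3.5 adds: "Unadjusted within-group changes (from baseline to postintervention) will be assessed using the paired t test".

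**The concern.** In the DIAL arm, study months 12-18 are the six months after the programme ends, so the window suits maintenance. In the wait list arm the same window opens six months into treatment. Its starting value is already an on-programme value, and the pre-DIAL value at month 6 plays no part in the contrast.

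At stake is the answer to a stated question of the delayed-start design: does DIAL raise activity again when the second arm receives it? If most of the gain comes early, a 12-18 change near zero could be taken as failure to replicate.

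The phrase in Section 8.3.5 does not settle the matter. If baseline means month 0 for everyone, the wait list change to postintervention runs from month 0 to 18. That adds six untreated months and starts at the visit closest to selection for under 60 minutes of activity a week (Section 4.1), so drift or regression towards the mean could be counted as a DIAL effect.

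With no contrast named in advance, 12-18, 6-12, 6-18 and 0-18 could each be reported as the replication result.

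**Working it through.** **1. Timeline.** In the wait list arm, programme month = study month - 6.

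- Study month 6: programme month 0, the last pre-DIAL visit.
- Study months 6 to 12: programme months 1-6 (daily calls, then twice a week).
- Study months 12 to 18: programme months 7-12 (weekly calls).

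Like-for-like pairs:

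| DIAL arm | Wait list arm |
|---|---|
| 0 to 6 | 6 to 12 |
| 0 to 12 | 6 to 18 |
| 6 to 12 | 12 to 18 |
| 12 to 18 (post-programme) | no visit in the plan |

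The primary aim tests the DIAL arm's changes from baseline to 6 and to 12 months. Their counterparts are the first two rows. The 12-18 change matches only the second half of the programme.

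**2. The plan's own figures (Section 8.2).** Two-group t test, difference 35, SD 90, two-sided 5%, 80% power: effect size 35/90 = 0.389 (the plan prints 0.388). The required n is 104.8, so 105 per arm, with 80.1% power. This reproduces.

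Paired test: the plan gives 35 minutes, SD 90, effect size 0.276, n = 105 and 80% power. Effect size 0.276 with n = 105 does give 80.0%. But 0.276 is not 35/90; it implies an SD of change of 35/0.276 = 126.8, close to 90 x sqrt(2) = 127.3. With an SD of change of 90, power at n = 105 would be 97.7%. Section 8.2 therefore supports two SDs, and both are carried forward.

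**3. Illustration for the wait list arm.** Inputs:

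- n = 120 x (1 - 0.15) = 102 (Section 8.2).
- Paired t test, two-sided 5%.
- SD of change 90 (as stated) or about 127 (implied).
- Assumed here, not in the plan: everyone takes up DIAL; the gain in programme months 1-6 is 35 minutes, as Section 8.2 assumes for the DIAL arm; activity then holds, or rises by a further 5 or 10 minutes.

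Noncentrality = (mean change / SD) x sqrt(102), on 101 degrees of freedom. For 35 minutes this is 0.389 x 10.10 = 3.93 with SD 90, or 0.276 x 10.10 = 2.79 with SD 127.

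| Window | Mean change | Power, SD 90 | Power, SD 127 |
|---|---|---|---|
| 6 to 12 | 35 | 97% | 79% |
| 12 to 18 | 0 (gain held) | 5% | 5% |
| 12 to 18 | 5 | 9% | 7% |
| 12 to 18 | 10 | 20% | 12% |

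If the gain is held, 6 to 18 has the same expected change as 6 to 12 and, at the same SD, the same power.

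**4. Sensitivity to the time course.** If a total gain of 35 minutes were split equally between the two halves of the programme, 6-12 and 12-18 would have equal power. If most of it came late, 12-18 would be the stronger of the two. The 6-18 contrast captures the whole gain under any split, which is why both month-6 contrasts are needed.

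**The case against.** Four objections have weight.

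- **The data are not lost.** A reader might infer that the trial cannot see the early wait list gain. The documents do not support that: activity is measured at months 6, 12 and 18 in both arms, and all visits enter the Section 8.3.2 model. The gain is missed by the contrast as written, not by the trial. This stands. However, the Tukey-Kramer comparisons in that section follow significant main effects, and they name no 6-12 or 6-18 contrast for this arm.
- **Section 8.3.5 is not the only other within-group analysis.** The mixed model and the paired test in Section 8.2 also exist. Nor does Section 8.3.5 say which visit is baseline for the wait list arm after it starts DIAL; month 0 to 18 is one reading, not a stated rule.
- **The power figures attach to a test the plan does not state.** No section specifies a paired test of the wait list change over months 12-18, or a criterion for replication. It is tempting to say that a programme performing as planned would appear not to replicate. That goes too far: Section 8.2 assumes 35 minutes at 6 months and says nothing about months 7-12. The figures are illustrative only.
- **The window may have been meant for maintenance alone.** The phrase about six months post-intervention can be read so, although the joint reading is the more natural one. On the narrower reading the replication aim has no window at all, and the same edit is needed.

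**Conclusion.** The point holds as a defect in how one contrast is specified. Study months 12-18 are the wait list arm's programme months 7-12, so that change cannot stand in for replication of the DIAL arm's 0-6 or 0-12 month effects. The matching changes are 6-12 and 6-18. This follows from the dates in Section 3.1 alone.

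The size depends on assumptions. With 102 participants, full uptake and a 35-minute early gain that is then held, power is about 79% to 97% over months 6-12 and 5% over months 12-18. A further 5 minutes in programme months 7-12 gives 7% to 9% over 12-18, and a further 10 minutes gives 12% to 20%. The ranges reflect the two SDs that Section 8.2 supports. A gain that came mainly late would reverse the ordering of 6-12 and 12-18, but would not make 12-18 a comparison with the pre-DIAL state.

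The point covers half of one exploratory aim. It should not be read as a finding about the primary analysis, which does not use this contrast.

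**What to change.** - **Sections 1.1 and 3.1:** split the aim. Keep the 12-18 month change for maintenance in the DIAL arm. Define replication in the wait list arm as its change from month 6 to 12, set beside the DIAL arm's 0-6 change, and from month 6 to 18, set beside the DIAL arm's 0-12 change.
- **Section 8.3.2:** name these as contrasts from the existing mixed model, reported as estimates with confidence intervals. The wait list 12-18 change can still be reported, labelled as its programme months 7-12.
- **Section 8.3.5:** state that month 6 is the wait list arm's pre-DIAL baseline for its change to postintervention.

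The cost is protocol and SAP wording, with the usual IRB review of an amendment. No visit, measure or participant is added. The edit should be made before the wait list follow-up data are examined.

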1.2 SCHEDULE OF ACTIVITIES (SOA)

2 INTRODUCTION

2.1 STUDY RATIONALE

The rates of physical inactivity and related cancer incidence and mortality are disproportionately high in the Deep South region in the United States, a rural, medically underserved region with a large African American population compared with the rest of the nation. Given this region's lower rates of literacy and internet access, interactive voice response (IVR) system—automated telephone-based interventions have the potential to help overcome physical activity intervention barriers (literacy, internet access, costs, and transportation) but have yet to be extended to rural, underserved populations, such as in the Deep South.

2.2 BACKGROUND

Our research team developed a tailored, IVR-supported physical activity intervention for cancer risk reduction in the Deep South. The development of the Deep South Interactive Voice Response System—Supported Active Lifestyle (DIAL) intervention was guided by extensive formative research (11 focus groups with African American community health advisors and community members) on physical activity intervention preferences and barriers in our target population. Results from the subsequent pilot randomized controlled trial with 63 participants supported the feasibility and acceptability of the DIAL intervention. Pilot trial findings and participant feedback guided intervention refinement (providing more accountability and encouragement) in preparation for scale-up.

2.3 RISK/BENEFIT ASSESSMENT

2.3.1 KNOWN POTENTIAL RISKS

The risks associated with the proposed study are minimal since a physical activity generally promotes good health, especially in a sample of healthy adults. Participants may find moderate intensity physical activity uncomfortable and may experience sprains, other soft tissue injuries, or bone injuries. However, risks associated with moderate intensity physical activity at Centers for Disease Control/American College of Sports Medicine recommended levels are rare. Due to the low level of risk, CDC/ACSM have recommended moderate intensity physical activity for adults with no prior history of cardiovascular risk or orthopedic impediments. Risk minimization protocol is derived from the American College of Sports Medicine's Guidelines for Exercise Testing and Prescription. Prior to enrollment, participants will be screened for cardiovascular risk factors and orthopedic problems affecting ability to safely perform moderate intensity physical activity. We will use an ACSM recommended screening instrument: Physical Activity Readiness Questionnaire (PAR-Q). The PAR-Q asks about cardiovascular and orthopedic risk factors for adverse events from moderate intensity physical activity.

After enrollment, participants will be provided with an exercise prescription that emphasizes safety with the following features: 1) training in assessing moderate intensity activity using a number of strategies (e.g., Rating of Perceived Exertion [RPE], target heart rate monitoring), 2) instructions to perform activity in the moderate range of exertion (i.e., 64% to 76% of maximal heart rate, 3) gradual increases in activity from week to week (i.e., 20% per week) until reaching the CDC/ACSM guidelines, 4) warm-up and cool-down as part of each activity, and 5) flexibility training after activity. These instructions will be provided as part of intervention orientation and each participant will also be provided with related written materials. Moreover, in each IVR call,

participants will be asked whether they have experienced any physical symptoms or complaints that could interfere with their physical activity program. If they respond 'yes' to this question, they are told to stop exercising and contact their personal physician to discuss the health issues further. The research staff will run weekly reports on reported health events and will follow up with a telephone call to the participant and discontinue physical activity intervention until physician clearance is provided. All health occurrences will be recorded and regularly reviewed by the study team and the UAB Institutional Review Board Office.

It is possible that specific survey items could be perceived as embarrassing or an invasion of privacy; thus, participants will be informed that they can refuse to answer any questions without penalty. Another unlikely risk is that, while the intervention is provided free of charge, participants may incur costs associated with the intervention (IVR calls) if using a cell phone with limited minutes plan. Participants will be cautioned against this risk by staff at the study information session and intervention orientation and staff will help participants with limited minutes problem solve how to conduct IVR calls without incurring costs (i.e., use landline) on a case-by-case basis.

2.3.2 KNOWN POTENTIAL BENEFITS

Regular physical activity is a key modifiable risk factor for several cancers (breast, colon).16 Since underserved (rural, African American) populations, particularly in the Deep South, report high rates of inactivity and are disproportionately affected by such cancers, they have even a higher likelihood of benefiting from receiving such physical activity interventions. However, no promise of a direct benefit will be made to the participants. Results from this study may be beneficial to future participants.

3 STUDY DESIGN

3.1 OVERALL DESIGN

The current study will test the efficacy of a 12-month multi-level, Interactive Voice Response system-supported physical activity intervention vs. a waitlist control condition. Primary endpoints are changes in moderate intensity or greater aerobic physical activity from baseline to 6 months and 12 months. Secondary endpoints include examining effects on physical performance and related psychosocial variables; intervention costs, changes in physical activity from 12-18 months, potential mediators/moderators of intervention efficacy, and barriers and facilitators to the implementation and sustainability of the DIAL intervention. This two armed randomized controlled trial will enroll a sample of 240 underactive adults from rural Black Belt (Marengo, Choctaw, Sumter, Hale, Greene, Dallas) counties in Alabama. Interested individuals will attend study information sessions hosted by local county coordinators to learn more about the study and complete brief screening interviews.

If still eligible and interested, participants will complete the informed consent process and be scheduled for an assessment visit. At this visit, participants will complete measurements (height, weight, waist circumference, 2 Minute Step Test, psychosocial surveys in REDCap) at a community location with their local county coordinator. Accelerometers will be distributed with instructions and a live demonstration of proper wear. Trained UAB staff will coordinate accelerometer data collection (device initialization, delivery, maintenance, etc). Participants will wear the accelerometer for 7 days. Once valid wear protocol is confirmed, participants will complete 7-Day Physical Activity Recall interviews by phone with trained, blinded UAB research

staff. After all assessment measures are complete, participants will be randomly assigned to a group. Intervention participants will receive orientation to the IVR system and begin the physical activity intervention and the Waitlist Control participants will be encouraged to maintain their normal routine until 6 month assessments. At 6-, 12-, and 18- months, participants will repeat accelerometer wear protocols, 7-Day Physical Activity Recall interviews (by phone), and inperson assessment visits (weight, waist circumference, 2 Minute Step Test, psychosocial surveys) with local staff. Psychosocial surveys will also be distributed at 3-months to a assess potential mediators/ moderators of treatment efficacy. Participants will also complete surveys and exit interviews to assess program satisfaction and solicit feedback for improvement (at 12 months for the intervention arm and 18 months for the waitlist control arm). The wait-control group will be offered the 12 month DIAL intervention (same as intervention arm) after the 6 month assessment.

Throughout the project period, UAB research staff and Office of Community Outreach and Engagement county coordinators will report study progress via weekly emails and Zoom meetings. Surveys and in-depth qualitative interviews with participating Office of Community Outreach and Engagement county coordinators will be held to reflect on barriers and facilitators to implementing IVR-supported cancer prevention interventions in rural Black Belt counties, as well as issues surrounding sustainability and future large scale dissemination.

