8.2 SAMPLE SIZE DETERMINATION

Results from our previous UAB pilot study indicated an increase in minutes of moderate-to-vigorous physical activity among the DIAL intervention group compared with the control group. The SD of this measure was 90 minutes. Assuming a mean difference of 35 (SD 90) minutes in moderate-to-vigorous physical activity between the two groups from baseline to 6 months, a two-tailed two-group t test, and a significance level of 5%, we will have 80% power to detect this difference (with an effect size of 0.388) with 105 participants per arm (210 for the study). Assuming a mean change of 35 (SD 90) minutes in moderate-to-vigorous physical activity from baseline to 6 months for the intervention group, a two-tailed paired t test, and a significance level of 5%, we will have 80% power to detect this within-group change (with an effect size of 0.276) with 105 participants. Allowing for 15% attrition, we will recruit 240 participants (120 per arm).

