8.3 STATISTICAL ANALYSES

8.3.1 GENERAL APPROACH

Analyses will be performed on an intent-to-treat basis (ie, participants will be analyzed by the arms to which they were randomized). All statistical tests will be two-sided. All analyses will be performed using SAS, and *P*<.05 will be deemed statistically significant.

Although a large amount of missing data is not expected for any of our study variables, a sensitivity analysis may be performed using alternative methods for handling missing data (such as multiple imputation) to assess the most appropriate approach based on the amount of missing data and effect sizes observed.

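### The 12-month primary comparison cannot test DIAL against an untreated control, because the wait list is offered DIAL after month 6

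*Combined protocol and SAP*

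**What the plan says.** - **Primary hypothesis and endpoints.** The primary aim in section 1.1 expects larger MVPA increases with DIAL "from baseline to 6 and 12 months than the wait list control arm". Section 3.1 describes a test of efficacy against a waitlist condition and states: "Primary endpoints are changes in moderate intensity or greater aerobic physical activity from baseline to 6 months and 12 months".
- **Control condition.** Section 3.1 says that "Waitlist Control participants will be encouraged to maintain their normal routine until 6 month assessments". It then says: "The wait-control group will be offered the 12 month DIAL intervention (same as intervention arm) after the 6 month assessment". Exit surveys and interviews fall at 12 months for the intervention arm and at 18 months for the wait list.
- **Analysis.** Under section 8.3.1, "participants will be analyzed by the arms to which they were randomized". Section 8.3.2 fits a repeated-measures mixed model to baseline, 6, 12 and 18 months with a group-by-time interaction. It does not say which visit's contrast tests the primary hypothesis. The only pairwise follow-up it names is Tukey-Kramer after significant main effects.
- **Sample size.** Section 8.2 is built on one time point: "Assuming a mean difference of 35 (SD 90) minutes in moderate-to-vigorous physical activity between the two groups from baseline to 6 months". No 12-month calculation is given.
- **Exploratory aim 2 (section 1.1).** Months 12 to 18 are to show maintenance in the intervention arm and replication of the effect in the wait list.

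**The concern.** At month 12 the control arm may have had up to six months of DIAL. Nothing in the plan keeps that arm off the programme until then, and nothing says what the 12-month contrast is meant to estimate. One of the two stated primary comparisons therefore cannot answer the question the primary aim asks.

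The risk is dilution and mislabelling, not a raised type I error rate. If both arms respond to DIAL, the 12-month difference shrinks, and it can vanish or reverse while the intervention is working. A reader who takes the primary aim at its word would see a small or null 12-month result as loss of efficacy against control, which this contrast cannot show.

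**Working it through.** **1. Who has received what by each visit (sections 3.1 and 5.1.2)**

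| Period | Intervention arm | Wait list |
|---|---|---|
| Months 0-6 | DIAL, first six months | Normal routine |
| Months 6-12 | DIAL, second six months | Offered DIAL, first six months |
| Months 12-18 | After DIAL | DIAL, second six months |

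Only the 6-month contrast has an untreated comparator. The call schedule sharpens the point: "Participants will complete IVR calls each day for 3 months, twice/week in months 4-6, and once/week in months 7-12". At month 12 the intervention arm is finishing the weekly phase, while wait-list participants who took up the offer have just come through the daily and twice-weekly phases.

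**2. The plan's own figure.** Inputs from section 8.2: difference 35 minutes, SD 90, two-sided 5%, power 80%. The normal approximation is n = 2 × (1.960 + 0.842)² × 90² / 35², which gives 104 per arm. The exact t-test solution is 104.77, so 105 per arm, as stated (power 80.1%). This applies to the 6-month contrast only. With 120 recruited per arm and 15% attrition, 120 × 0.85 = 102 are analysed, and power is 78.9%.

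**3. The 12-month contrast under crossover.** Let r be the share of the 35-minute effect that the DIAL arm keeps at month 12, and g the wait list's gain on DIAL as a share of 35 minutes. Neither is in the documents, so both are assumptions.

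Expected difference = 35 × (r − g). Crossover removes 35 × g minutes whatever r is.

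With SD 90 and 102 per arm, the standard error is 90 × √(2/102) = 12.60 minutes. The 95% confidence interval half-width is 1.972 × 12.60 = 24.85 minutes. Power is from the noncentral t distribution, two-sided 5%.

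Full effect kept (r = 1):

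| Wait-list gain g | Expected difference (min) | Two-sided power | Analysed n per arm for 80% |
|---|---|---|---|
| 0 | 35 | 79% | 105 |
| 25% | 26.25 | 55% | 186 |
| 50% | 17.5 | 28% | 417 |
| 75% | 8.75 | 11% | 1,662 |
| 100% | 0 | 5% (false-positive rate) | none suffices |

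At g = 100% the expected interval is about −25 to +25 minutes, although DIAL works in both arms.

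**4. If the DIAL effect fades.** For g = 0, 25, 50, 75 and 100%, the chance of a significant result *in DIAL's favour* (one direction only, unlike the table above) is:

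- r = 0.75: differences 26.25, 17.5, 8.75, 0 and −8.75 minutes; chances 55%, 28%, 10%, 2.5% and 0.4%.
- r = 0.5: differences 17.5, 8.75, 0, −8.75 and −17.5 minutes; chances 28%, 10%, 2.5%, 0.4% and below 0.1%.

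**5. Other inputs.** With r = 1 and g = 50%, power is 34% for SD 80 and 24% for SD 100. With SD 90 it is 27% at 20% attrition (96 per arm) and 25% at 25% attrition (90 per arm).

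**6. Exploratory aim 2.** From the table in step 1, the wait list's counterpart to the intervention arm's months 0-6 is its months 6-12. Its months 12-18 correspond to the intervention arm's months 6-12. The aim's 12-18 month window therefore misses the wait list's first six months on DIAL.

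**The case against.** **The wait might end at month 12.** Section 1.1 read alone would be coherent if it did: a controlled comparison to 12 months, then replication in months 12-18. This reading does not survive. Section 3.1 is the only explicit statement of timing, and it says after the 6-month assessment. The 18-month wait-list exit survey fits a 6-18 month treatment window. A 12-month programme begun at month 12 would end at month 24, beyond the 18-month subject duration in section 1.1.

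**The hypothesis names a wait list, not an untreated control.** Literally, a greater increase to 12 months in the arm randomized to DIAL can be tested by intention to treat. That stands, and it is why the comparison remains valid as immediate versus delayed start. But both sections frame it as efficacy, which invites the stronger reading.

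**Offered is not the same as taken up, and the sizes are assumed.** Also true. Zero gain is in the range, and the figures are illustrations, not bounds. They come from a t test, not from the planned mixed model with covariates. The direction of the dilution does not depend on them.

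**Readers will have the 6-month and within-arm results beside it.** These make a misreading avoidable, but they do not alter what the primary aim claims at 12 months.

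**Changing a primary endpoint late is itself a risk.** This stands, and it limits the remedy.

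**Conclusion.** The concern holds. Followed exactly, the plan yields a 12-month contrast of immediate versus delayed start under the name of efficacy against control. Every minute the wait list gains on DIAL by month 12 is a minute lost from that contrast.

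The direction is certain wherever the wait list benefits at all. The amount is not, because uptake, wait-list response and durability in the DIAL arm are all unstated. Across no to full wait-list response with the DIAL effect fully kept, power runs from 79% down to the 5% error rate. With fading, the expected difference can turn negative.

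The crossover leaves the 6-month contrast intact; other aspects of that contrast were not examined here. The plan already leans on month 6: the sample size uses it, and the cost-effectiveness comparison with no active intervention in section 8.3.3 has a 6-month time frame. The wording should be corrected before outcomes are analysed by arm.

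**What to change.** 1. **Sections 1.1 and 3.1.** Make change in MVPA from baseline to 6 months the primary DIAL-versus-wait-list efficacy comparison. Keep the 12- and 18-month results, labelled as immediate versus delayed start (between arms) or as within-arm maintenance.
2. **Section 8.3.2.** State that the primary hypothesis is tested by the group contrast in 6-month change from the mixed model, whether or not a main effect is significant. Name the outcome as 7-Day PAR minutes, in line with the endpoint in section 1.1 ("Changes in physical activity (as measured by 7-Day Physical Activity Recall" interview), with the accelerometer as corroboration, as section 8.1 has it.
3. **Exploratory aim 2.** Reconcile it with the crossover in section 3.1. Report the wait list's changes over months 6-12 and 12-18 as uncontrolled within-arm changes, not as replication of a randomized effect.

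**Cost.** No new data, visits or participants. The stated primary aim changes, so the Statement of Compliance requires IRB approval first, and the amendment should precede any analysis of outcomes by arm. Section 3.2 gives 2024-11-26 as the final primary-outcome collection date, and the documents do not show whether such analysis has begun. If it has, leave the endpoints as stated, and label and interpret the 12-month contrast as immediate versus delayed start in the report; a late switch of primary endpoint would cost credibility. The sponsor gives up only a 12-month claim of efficacy against control that this design cannot support.
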